Both pharmacotherapy, CBT-I (or BBT-I) and their combinations produce treatment response only in 60-67% of patients and remission only in 42-55%. A reasonable way to improve the clinical effectiveness is determining the target group of patients that benefits most of iCBT-I. Some studies have shown that efficacy of CBT-I is related to the severity of maladaptive cognitions and behavior. As there is not much knowledge about predictors of iCBT-I treatment efficacy, in this trial, we will deliberately analyze psychometric, anamnestic and sleep characteristics which may act as predictors of CBT-I, which may also be relevant in iCBT-I. Specifying predictors of effectiveness of iCBT-I will give the opportunity to develop more individualized therapeutic decision-making procedure and will be important for economic reasons. In the longer term, obtaining of portrait for patient who benefit from iCBT-I will give us cues to understanding insomnia in whole and its subtypes.

It would be the first implementation of on-line behavioral treatment for insomnia in Russia and the first attempt to develop online materials for chronic insomnia treatment which would simplify the insomnia treatment improve patient adherence. In view of a huge demand of specialists in CBT-I development and approbation of this program will fill this gap in clinical practice. All the participants will have access to care as usual (CAU), which let us reconstruct real clinical situation along the whole course of the study. To our knowledge, this is one of the first studies considering iCBT-I in clinical settings.

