1.2. PREVIOUS CLINICAL APPLICATION

Structure of the investigated treatment course Internet-based CBT-I (Sleepsy[©]) is based on the already established program iSLEEP – internet-based self-help against insomnia that was already tested in previous study in Bern Universitz, Switherland. Short-term effectiveness of iCBT-I was high with effect size from median to large. The longest follow-up period in the studies of iCBT-I was 3 years. After this period there was no difference in the primarz outcomes between intervention and control group, but participants of intervention group used sleep aids significantky less than control. Moreover, there were no adverse events throughout the follow-up

Since the overwhelming majority of iCBT-I randomized controlled trials (RCTs) were conducted in research settings with recruitment via internet and advertisement, it is unclear if the promising results from efficacy studies can be transferred to routine clinical practice. For this study participants will be recruited from the doctor's office to ensure proper diagnostics and exclusion of other diseases affecting depth and length of sleep. It may be that patients, referred to iCBT-I directly from doctor's office, have active and more severe sleep complaints, and therefore are more motivated to benefit from the treatment

2. Aim of the study

Aims:

1. to investigate clinical effectiveness and cost-effectiveness of the internet-based CBT-I program Sleepsy in comparison with care as usual (CAU) among patients with CI recruited from clinical settings.

2. to investigate predictors of treatment outcome by analysis of baseline characteristics.

Tasks:

[figure not shown]
- Baseline assessment of recruited participants;
- Randomization;
- Treatment of intervention group by means of iCBT-I course;
- Post-treatment assessment of all participants;
- Follow-up assessment of all participants;
- Comparison of primary and secondary outcomes in intervention and control groups;
- Treatment of control group by means of iCBT-I course;
- Post-treatment assessment of control group participants;
- Statistical analysis of response predictors.

Hypothesis

- iCBT-I is more effective and cost-effective than CAU in clinical settings
- The analysis will help us identify the typical sleep pattern and obtain psychological portrait of those who benefits from behavioral treatment

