3. STUDY DESIGN

- a) The proposed study is a multicenter parallel-group add-on superiority RCT comparing an active treatment condition (iCBT-I plus CAU) to CAU alone.

After signing the IC form, participants will receive an e-mail with the link to the Qualtrics Survey Software (Qualtrics, Provo, UT, USA), where they complete baseline assessment and receive the individual allocation code. On completion of baseline measures, subjects will be automatically assigned by the randomization function of Qualtrics Survey Software to either iCBT-I plus CAU or CAU group using single block randomization. Neither participants nor referring specialist nor the research team have foreknowledge and/or control over randomization and the allocation procedure. Following randomization, the participants will receive an automated email regarding their group allocation and a description of future steps. In case they were allocated to the treatment group, their individual code will provide an access to the iCBT-I program.

Participants in the control group will get access to the iCBT-I program after the 5-month follow-up (3 months after post-assessment) provided they completed the follow-up assessment and still fulfill eligibility criteria. In this group, an additional assessment will be conducted eight weeks after providing access to the CBT-I program to enlarge the sample for the analysis of outcome predictors.

The research team, except the trial coordinator, will be blind to allocation. Coding allocation form, along with the participant's real name and address noted in the IC form, will be stored in the password-protected computer of the trial coordinator. Participants will not be blind to treatment allocation and will receive information about their randomization outcome via email. Questionnaires and sleep diaries will be completed entirely online under the participant's individual code.

3.1.OUTCOMES

3.1.1. The primary endpoint of the present study is the change of Insomnia Severity Index (ISI) from pre- to post-treatment and at follow-up.

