Module 4: Sleep hygiene and stimulus control: Information on sleep-inhibiting substances, sleep-wake-rhythm, evening rituals, physical exercise, etc., as well as information on the principle of stimulus control with the aim of re-associating the bed with sleep.

Module 5: Progressive Muscle Relaxation (PMR) based on Jacobson with audio tape and written instruction to download.

Module 6: Cognitive restructuring: Identifying, reexamining and changing dysfunctional thoughts about sleep and the consequences of insomnia.

Module 7: Relapse prevention: what to do to prevent sleep disorders or when the sleep disturbances come back, when to seek medical help and what are the conditions of safe pharmacotherapy for insomnia.

Module 8: Repetition and end.

The program includes a sleep diary in which participants insert data on their bedtime and waketime, sleep latency, total sleep time, and night awakenings. The data entered into the sleep diary are then presented in form of graphs. Furthermore, various exercises serve to put what is learnt into practice. Participants have time to repeat, deepen and apply modules, exercises and examples in their everyday life at their own pace, i.e., the

participants are free to choose when and how often they process the modules and whether they process them in one piece or in several stages. Patients will get behavioral instructions based on their questionnaires, sleep diary, and answers in the interactive part of the program. A sleep window will be proposed depending on the preferred wake-up time and average total sleep time over the last 7 days. If the sleep diary indicates a sleep efficiency of 85% or higher for the previous week, the participant will be encouraged to add 15 min to the sleep window. If it does not reach the 85%, recommended sleep window will be decreased based on the preferred wake-up time and average total sleep time over the period of observation. If the sleep efficiency falls between 80% and 85% sleep window will remain stable otherwise (sleep efficiency > 85%) it can be extended by 15 min. All material will be delivered through the internet program and expected to be elaborated by the patients themselves but with the opportunity to contact a psychologist or somnologist within the program (guidance on request) in a secured environment

The program was elaborated by [name], M.D., Ph.D., associate professor, Sechenov university. M.D., D. [name], M.D., Ph.D. [name].

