9. STATISTICAL ANALYSIS

9.1. SAMPLE SIZE CALCULATION

We aim to detect a small to medium between-group effect size (Cohen's d) of 0.35 at post-treatment. The chosen effect size is reasonable since CAU being an active alternative treatment may decrease between-group outcome differences and a smaller effect size was considered to be irrelevant from a clinical point of view. Based on a-level of .05 and a power of .95 using a single-level repeated measures ANOVA power analysis with G*Power, the sample size needed is approximately 55 participants per group and 110 for the total sample. Our secondary aim is to find outcome predictors within participants who complete iCBT-I. In order to enlarge this sample, participants from the CAU group will get access to the iCBT-I program after the follow-up period.

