9.2. STATISTICAL ANALYSIS OF EFFECTIVENESS

The main analyses will be conducted on the intention-to-treat sample. Clinical effects of treatment will be evaluated using mixed-model repeated-measures analyses where the pre-post comparisons of all outcome measures will include time as a within-group variable and the condition as a between-group variable. An incremental cost-effectiveness ratio (ICER) will be calculated to obtain the additional costs of iCBT-I in comparison with control condition. Cohen's d will be reported for all within-between comparisons based on estimated means and the pooled standard deviation from the observed means at pre- and posttreatment. To test significance of the difference between the number of responders in each treatment condition, we will use χ^2 -test. Regression analyses will be used to identify predictors of treatment outcome. We will test models using Akaike/Bayesian Information Criteria to select an optimal model with predictors of treatment outcome.

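### The outcome-predictor analysis is confined to people who complete iCBT-I, which would hide baseline traits that reduce benefit by making patients quit

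*Combined protocol and SAP*

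**What the plan says.** Section 2 gives the second aim as "to investigate predictors of treatment outcome by analysis of baseline characteristics" and names no population. Section 9.1 does name one: "Our secondary aim is to find outcome predictors within participants who complete iCBT-I". It adds that CAU participants get the program after follow-up so that this sample grows. Section 3 repeats the purpose ("to enlarge the sample for the analysis of outcome predictors") and limits crossover to controls "provided they completed the follow-up assessment and still fulfill eligibility criteria".

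In Section 9.2, "The main analyses will be conducted on the intention-to-treat sample", but that sentence covers the main analyses. For the predictor work the section says "Regression analyses will be used to identify predictors of treatment outcome", with AIC/BIC model selection. It gives no population, no rule for missing outcomes and no treatment of non-completers.

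The Background gives the purpose as "determining the target group of patients that benefits most of iCBT-I", in support of individualised treatment decisions. Section 4 describes a self-paced program with guidance on request: "participants are free to choose when and how often they process the modules". Section 3.1.2 logs modules completed, time on the site, diaries and use of support, but sets no threshold for completion.

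**The concern.** Whether to offer iCBT-I is decided before anyone knows who will finish it. An analysis of finishers answers a narrower question: who improves, given completion. The candidate predictors (beliefs about sleep, sleep hygiene, mood, expectancy, personality) could plausibly influence who finishes a self-paced course. If a trait reduces improvement mainly by leading people to stop, removing those who stopped removes the evidence. The trait would be reported as unrelated to outcome, although it matters at the point of referral.

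The filter also works against the crossover, which was added to enlarge this sample. At most 110 people can be given access; at an assumed 50% to 80% completion, 110 × 0.50 = 55 to 110 × 0.80 = 88 remain.

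**Working it through.** **The plan's own figure.** No sample size is stated for the predictor analysis. The total of 110 in Section 9.1 reproduces as a repeated-measures ANOVA interaction: f = 0.35/2 = 0.175, two groups, two time points, correlation 0.5 (assumed; none is given). λ = 0.175² × 110 × 2/(1 − 0.5) = 13.48, power 0.953. Here 110 matters only as the ceiling on people given access, because crossover controls must also complete T2 and remain eligible.

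**Hidden predictor.** Assumptions, none from the documents: a standard normal trait X; completion C logistic in X with odds ratio 0.5 per SD; improvement = 3 + 5C + noise with SD 5 (so 8 points for completers, 3 for others).

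- Slope among all given access = 5 × Cov(X, C) = 5 × ln(0.5) × E[p(1 − p)], where p is the completion probability given X.
- Residual variance = 25 + 25 × c(1 − c) − slope², with c the overall completion rate. SE = √(variance/110).
- Slope among completers = 0, because C is constant there and X has no other route to outcome. The zero follows from the assumed mechanism; it is not an empirical result.

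| Completion | E[p(1 − p)] | Loss of improvement per SD, all given access | Residual variance | SE, n = 110 | Power, two-sided 5% | Completers |
|---|---|---|---|---|---|---|
| 50% | 0.2254 | 0.78 | 30.64 | 0.53 | 31% | 0 |
| 60% | 0.2171 | 0.75 | 30.43 | 0.53 | 29% | 0 |
| 70% | 0.1918 | 0.66 | 29.81 | 0.52 | 24% | 0 |
| 80% | 0.1487 | 0.52 | 28.73 | 0.51 | 17% | 0 |

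First row: 5 × 0.693 × 0.2254 = 0.78; 25 + 6.25 − 0.61 = 30.64; √(30.64/110) = 0.53. These values come from numerical integration; simulation with 2,000,000 draws per setting agrees to about 0.01 (0.79, 0.76, 0.67, 0.52). At 90% completion the slope is 0.30.

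**False predictor.** Assumptions: X has no effect on outcome; completion depends on X (odds ratio 0.5) and on an unmeasured motivation U (odds ratio 2); ISI change = −6 − 2U + noise with SD 4.5. Among all given access the slope on X is 0. Among completers, by simulation:

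| Completion | Completers of 110 | Slope per SD | SE | False-positive rate |
|---|---|---|---|---|
| 50% | 55 | −0.18 | 0.69 | 5.8% |
| 60% | 66 | −0.17 | 0.63 | 5.8% |
| 70% | 77 | −0.15 | 0.58 | 5.7% |
| 80% | 88 | −0.11 | 0.54 | 5.5% |

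The bias is about a quarter of one SE. Here U correlates with outcome at 2/√(4 + 20.25) = 0.41. In a second model with that correlation raised to 0.7, and loadings of 0.5 and −0.5 on liability to quit, the false-positive rate among completers is 7% to 15% as completion falls from 90% to 50%. Size therefore depends heavily on assumptions.

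**The case against.** **The word may be loose.** A reader might infer that Section 9.1 fixes a firm completer filter. The documents do not settle that. The same passage enlarges the sample by giving access, Section 3 times the extra control assessment from access rather than from finishing modules, and neither aim 2 nor Section 9.2 repeats the restriction. Completing may have been meant as receiving. This stands as a caveat, but Section 9.1 is the only statement of the predictor population and nothing overrides it. An analyst following it would drop non-finishers at a threshold not set in advance.

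**The illustration is built to show the effect, and the remedy has little power.** Both are true. Power of 17% to 31% means the wider analysis would usually miss such a trait too. It would, however, be estimating the right quantity.

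**False predictors.** A reader might infer that the filter will fill the results with spurious predictors. Under the first set of assumptions the false-positive rate barely moves from 5%, and the larger rates need a much stronger unmeasured factor. This is a minor part of the point.

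**Those who quit may not supply outcomes.** T1 is scheduled for everyone randomised, but stopping the modules and not answering the questionnaires may go together, and Section 8.5 provides no further monitoring of people who drop out of the study. Some values would then be imputed. This stands and should be reported openly.

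**Completer results are of interest.** They are, as an answer to the narrower question, and can be kept in that role.

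**Conclusion.** The point holds for the secondary aim. The only stated predictor population is selected on an undefined event that follows the start of treatment, and this does not match the Background's purpose of choosing whom to treat. The main risk is that traits acting through quitting are hidden: in the illustration, 0.78 to 0.52 ISI points per SD at 50% to 80% completion is lost entirely. That size rests on assumed completion rates, an assumed 8-versus-3-point contrast and an assumed odds ratio. The false-predictor risk is real in principle but small in the base illustration.

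Two stronger inferences are not supported. The primary comparison is not compromised: it is planned on the intention-to-treat sample, and neither it nor the total of 110 depends on this restriction. Nor would widening the population show who benefits relative to CAU. The pooled regression is uncontrolled, and controls treated after week 20 have no randomised comparator, so it shows who improves after being offered iCBT-I.

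**What to change.** In Sections 9.1 and 9.2:

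- Define the predictor population as all participants given access to iCBT-I, whatever number of modules they complete.
- Use the ISI eight weeks after access (T1, or T3 for crossover controls), with the last assessment before access as baseline (T0, or T2 for crossover controls). Expectancy and the general questions are scheduled only at T0, so say that T0 values are used for these.
- Include a term for cohort and also show crossover controls separately, since they are selected on completing T2 and on continued eligibility.
- Handle missing ISI by the mixed model or multiple imputation, and report how many non-completers supplied it.
- Model the number of modules completed as a separate outcome with the same predictors.
- Keep the completer model as a sensitivity analysis, with completion defined in advance by number of modules.
- State that the results describe improvement after being offered the program, not benefit relative to CAU.

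The cost is revised wording and one extra regression; the assessments and module logs are already planned. The downside is that slopes describe being offered the program, may be weaker for traits that act only through use, and rest partly on imputed values if those who quit do not respond.

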7.1. INCLUSION CRITERIA

1. Age between 18 and 80 years
2. Sleep disorder matching CI criteria (International Classification of Sleep Disorders-3) — assessed by clinical judgement
3. Ability to follow the procedures of the study, fluent Russian language, good access to internet — assessed by self-report

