7.3. EXCLUSION CRITERIA

1. Refusal of the further participation;
2. Pregnancy
3. Exacerbation of Anxiety or depressive disorder as measured with the Beck Depression Inventory (BDI-II; score > 28) and the Beck Anxiety Inventory (BAI; score > 25)—assessed by the questionnaires at any timepoint
4. Increase of suicidality risk — as measured with BDI-II suicidality subscale score >1 at any timepoint

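### The predictor regression pools immediate iCBT-I completers with controls still eligible after 20 weeks of CAU, and section 9.2 names no term to separate the two cohorts

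*Combined protocol and SAP*

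**What the plan says.** Section 9.1 (Sample size calculation) defines the predictor aim: "Our secondary aim is to find outcome predictors within participants who complete iCBT-I". To increase the number available, "participants from the CAU group will get access to the iCBT-I program after the follow-up period".

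Section 3 (Study design) gives the operating rule. Controls are offered the program after the week-20 assessment (T2), "provided they completed the follow-up assessment and still fulfill eligibility criteria". They are assessed again eight weeks later (T3, week 28), and the stated purpose is "to enlarge the sample for the analysis of outcome predictors".

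Two parts of the eligibility rules bear on who passes the week-20 re-check:

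- Section 7.1 requires "Sleep disorder matching CI criteria (International Classification of Sleep Disorders-3"), so a control whose insomnia has resolved no longer qualifies.
- Section 7.3 removes participants above the BDI-II or BAI cut-offs, "assessed by the questionnaires at any timepoint", so some controls who have worsened are out as well.

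On the analysis, section 9.2 says: "Regression analyses will be used to identify predictors of treatment outcome". AIC or BIC then chooses among models. No cohort, arm-of-origin or period term is named for this regression. The condition factor in 9.2 belongs to the mixed model for effectiveness, not to the predictor model.

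**The concern.** The two parts of the predictor sample reach iCBT-I by different routes. Immediate-arm patients start at entry. Delayed patients start only if they stayed in the study to T2 and still qualified after 20 weeks of CAU, which section 9.1 itself treats as an active alternative. A trait that goes with persistence under CAU will be more common in the delayed cohort. If that cohort also gains more or less from iCBT-I on average, a pooled regression without a cohort term assigns part of the difference to the trait. This is confounding by cohort. Choosing T2 rather than T0 as baseline for the delayed patients would not remove it.

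Prediction is the second of the two aims in section 2, and the Background intends the predictors to support individual treatment decisions. The risk is that a marker of persistence under CAU is reported as a marker of poor response to iCBT-I.

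**Working it through.** **The plan's own figure.** The only stated sample size is 110, for the between-group comparison. It reproduces as a repeated-measures ANOVA within-between interaction with f = 0.35/2 = 0.175, 2 measurements and an assumed correlation of 0.5: λ = N·m·f²/(1−ρ) = 110 × 2 × 0.030625/0.5 = 13.475, power 0.953. No figure is stated for the predictor sample, so there is none to reproduce.

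**Inputs.**

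- From the plan: 55 per arm.
- Assumed: the share of controls retained at week 20. The Background says that drugs, CBT-I or BBT-I, and their combinations "produce treatment response only in 60-67% of patients and remission only in 42-55" per cent. Borrowing the remission range for CAU, as an upper assumption, gives retention of 1 − 0.55 = 45% to 1 − 0.42 = 58%, that is 55 × 0.45 = 24.75 to 55 × 0.58 = 31.9 controls. A milder case is 80%, or 44 controls.
- Assumed: a cohort difference in iCBT-I outcome of 0.5–1.0 SD, and a trait linked to non-remission with log-odds 0.5 (moderate) or 1.0 (strong) per SD. The documents give neither.

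**Mechanism by hand.** Take 60% retention, a trait correlated 0.5 with persistence, no effect of the trait on iCBT-I gain, and delayed patients gaining 0.8 SD less.

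- Mean trait among retained controls: 0.5 × φ(−0.253)/0.60 = 0.5 × 0.644 = 0.322.
- Pooled N = 55 + 33 = 88; delayed share 33/88 = 0.375.
- Covariance of trait with cohort: 0.375 × 0.625 × 0.322 = 0.0755.
- Trait variance in the retained controls: 1 − 0.25 × 0.644 × (0.644 + 0.253) = 0.856. Pooled: 0.625 + 0.375 × 0.856 + 0.2344 × 0.322² = 0.970.
- Spurious slope: −0.8 × 0.0755/0.970 = −0.062. Simulation gave −0.061.
- Standard error: √(1 + 0.2344 × 0.64)/√(88 × 0.970) = 1.072/9.24 = 0.116, so the shift is 0.062/0.116 = 0.54 standard errors.
- Rejection rate: Φ(−1.42) + Φ(−2.50) = 0.078 + 0.006 = 0.084. Simulation gave 0.080.

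**Simulation at 60% retention** (4,000 repetitions per cell; ranges are over trait correlations 0.3, 0.5 and 0.7):

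| Delayed cohort gains less by | No cohort term | With cohort term |
|---|---|---|
| 0 SD | 0.051–0.055 | 0.046–0.054 |
| 0.35 SD | 0.049–0.066 | 0.047–0.053 |
| 0.5 SD | 0.058–0.069 | 0.046–0.054 |
| 0.8 SD | 0.067–0.117 | 0.047–0.052 |

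The Monte Carlo standard error near 5% is √(0.05 × 0.95/4000) = 0.0034.

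**Simulation with the logistic link, cohort difference 0.5–1.0 SD.** At 45–58% retention, the rejection rate for a null trait is 5–7% (moderate link) and 6–12% (strong link). With a cohort term it is about 5%. At 80% retention without the term it is about 4–7%.

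**Under the plan's selection rule.** AIC admits one extra term when the likelihood-ratio statistic exceeds 2. For a null trait in a homogeneous sample this happens with probability P(χ²₁ > 2) = 0.157. At 45–58% retention without a cohort term, inclusion rises to 17–29%; with the term it returns to about 16%, not to 5%. BIC's threshold is ln N, which is ln 80 = 4.38 to ln 87 = 4.47. That is somewhat stricter than the 3.84 of a 5% test, so the 5% results are a rough guide to BIC.

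**Limit of the check.** The simulations keep all 55 immediate patients. The plan's predictor population is completers, and completion is not modelled.

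**The case against.** Much of the case on the other side stands, and it limits the point.

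- A reader might infer that 9.1 and section 3 define the added population in conflicting ways. They do not. Section 9.1 speaks of participants from the CAU group, not all of them, and summarises a rule set out in section 3. Section 3.2 likewise confines T3 to controls who complete follow-up and are then offered the program.
- A reader might infer that the predictor sample falls short of a promised 110. Section 9.1 promises no predictor sample size.
- A reader might picture the immediate cohort as 55 unselected referrals. Section 9.1 limits the aim to completers, so that cohort is selected too, in a different way.
- Naming no cohort term is not the same as ruling one out. Section 9.2 names no covariates at all for this regression.
- The strength of the week-20 filter is unknown. The insomnia criterion rests on clinical judgement, no clinic visit is described at T2, and the Background's remission range is not for CAU.
- Applying the same entry criteria to both cohorts when iCBT-I starts is a defensible choice.
- The upper figures need a strong link, heavy loss of eligibility and a large cohort difference together.

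None of this removes the mechanism. An under-specified model chosen by AIC/BIC may drop a cohort term even if the analyst thinks of one, which is a reason to fix it in advance.

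**Conclusion.** The point holds as a minor, inexpensive improvement to a secondary aim. The documents establish the pooling, the week-20 re-screen and the absence of a named cohort term. They do not establish the size of the distortion, which depends on three things they do not supply: the share of controls still eligible, the difference in iCBT-I response between cohorts, and the trait's link to persistence. It ranges from nothing, when the cohorts respond alike, to roughly a doubling of the 5% error rate in the most adverse combination examined. A cohort term removes the excess due to pooling; it does not lower AIC's ordinary tendency to admit null predictors. A reader might also infer that the efficacy result is compromised. It is not: the randomised comparison through T2 does not use the delayed iCBT-I data.

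**What to change.** In section 9.2, state that a fixed indicator for cohort (immediate versus delayed iCBT-I) is kept in every candidate predictor model and is not subject to AIC/BIC selection. State also that each retained predictor will be re-estimated in the immediate cohort alone as a sensitivity analysis.

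In section 9.1, repeat the section 3 condition and describe the added participants as controls who completed T2 and remained eligible after 20 weeks of CAU. This is a clarification of wording only; no sample size changes.

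The cost is one degree of freedom in the predictor model, one extra set of estimates, and a few lines of text. No new data, visits or participants are needed.
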